1. Referrals from VA health providers, including primary care providers, geriatricians, endocrinologists, and other subspecialist who care for diabetic patients.
2. Direct advertisement through local newspaper and at the VA for potential subjects.
3. Referrals from the VA Ann Arbor MOVE! program. The MOVE! program in VA Ann Arbor provided care for 710 veterans in 2010, with 490 of them as first time participants in MOVE! program;⁶¹ 50% of the MOVE! participants have diabetes.⁶²
4. We will obtain VA Institutional Review Board's approval to screen for diabetic patients using the VA electronic medical record. After identifying potential subjects, we will contact their primary providers for approval to recruit these patients.

Sample:

[figure not shown]
We will recruit approximately 70 veterans who have known diabetes and are aged ≥ 60 years. Subjects will be recruited based on their self-reported diabetes diagnosis. After identifying potential subjects, we will send them introductory letters describing the study, including an opt-out postcard for them to mail back. If we do not receive the opt-out postcard after 2 weeks, then we will contact the veterans by phone to confirm their interest in participating in the study and to screen for eligibility.

Eligibility

Inclusion Criteria

- Aged ≥ 60 years
- Diagnosis of diabetes mellitus, type 2 (or adult-onset) (self-reported or per medical record)
- At least 5/6 on 6-item cognitive screening test on the phone
- Ability to reliably operate the Actiwatch accelerometer
- Community-living (i.e., not nursing home resident)
- Ambulatory either with or without an assistive device
- English-speaking
- Competent to provide informed consent
- Sedentary (< 150 min moderate activity in a week)

Figure 3.

Exclusion Criteria

- Medically unstable in which exercise would be contraindicated (e.g., previous severe symptomatic hypoglycemia, decompensated congestive heart failure, severe anemia, severe aortic stenosis, unmanaged thyroid dysfunction, etc.)
- Self-reported illness or conditions that impair cooperation with the study team or ability to complete study procedures
- Hospitalization within last 6 months for any reason
- 2 or more days of complete bed rest within the last month
- Limb hemiplegia or amputation
- Replacement of any hip or knee joint within the last 6 months
- Current attendance in a PA program
- Work involves shift schedule
- Heart attack within past month
- Parkinson's disease

PARTICIPANT TIMELINE

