b) **Social participation** will be measured from the 2 sources (*Please see Appendix for questionnaire*): **Social participation** will be measured at each assessment point using validated questionnaires from the Patient-Reported Outcomes Measurement Information System (PROMIS) assessment center.⁷⁷ Together, these questions (51 items) assess two subdomains of social participation - *ability to participate* and *satisfaction with participation*.⁷⁸ Each set of the questionnaire can be administered independently and have been validated and standardized with a population mean of 50 and standard deviation 10. PROMIS assessment center also offers shorter versions of social participation questionnaires.

PROMIS is a NIH initiated multicenter cooperative group who builds and validates common, accessible item banks to measure key symptoms and health concepts applicable to a range of chronic conditions, enabling efficient and interpretable clinical trial and clinical practice applications of patient-reported outcomes. These patient-reported outcomes are built on the WHO framework of physical, mental, and social health, and social participation is one of the key domains included in PROMIS items. The item banks all underwent rigorous psychometric evaluation, and are broadly available for use in clinical research and clinical practice.

1. **Satisfaction with participation**, the subdomain of social participation most consistent with quality of life, will be additionally investigated to see if it fluctuates daily and if it is associated with daily PA level. We will adapt three questions from the PROMIS item bank and ask the participants to record their ratings (1-5) into the logbook daily during the 7-day home monitoring periods: "I am satisfied with my current level of social activity; I am satisfied with my ability to perform my daily routines; and I am satisfied with my ability to do leisure activities."

Secondary outcomes:

a) **Functional status** will be assessed by 2 physical performance measurements and 1 self-reported physical function status, all commonly used and validated. Changes in these 3 measurements may be clinical meaningful to predict fall risks, ability to live independently and mortality.^{79,80} Based on the study enrollment criteria, we do not anticipate any participants to have limitations in instrumental or basic activity of daily living, so these basic functions will not be assessed to minimize their burden.

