 - a) Measure of the Quality of the Environment (MQE) version 2.0³⁷ is one of the most comprehensive measurement instruments that address specific ICF categories of environmental factors.⁸⁸ (See Appendix) This level of detail information is important for our intervention as it involves using strategies to overcome the environment barriers within the individual's daily life routines. MQE assesses 2 domains of environment that are most relevant to the proposed study: physical environment (40 items) and social environment (69 items). It also assesses an individual's perception of the environment on his/her ability to accomplish daily activities or tasks and social roles. The perception is rated on a 7-point Likert scale ranging from -3 (major obstacle) to 3 (major facilitator). Therefore, MQE produces 2 levels of data: 1) number of self-perceived environment barriers/facilitators, and 2) the perceived level of influence a barrier/facilitator on the person.
 - b) Momentary assessment of the environment will be obtained through the Actiwatch prompting the participant to record their perception of the environment on their ability to participate in PA and social activities. This method of obtaining immediate-recalled data (vs., delayed recall) in natural settings, ecological momentary assessment (EMA), is a new research method that the PI will be learning from her mentors, and the momentary information obtained will be exploratory, but important in informing the intervention to target those barriers that have the most impact on the activities. To our knowledge, this method has not been used in lifestyle interventions in our study population. During the baseline 7-day home monitoring period, the study participants will enter their perception of the physical and social environment, into the accelerometer 5 times a day. The questions for the participants will be the following:
 1. "Considering your current surroundings, indicate to what extent do they hinder you or prevent you from being physically active?" Answers range from 0 to 10.
 2. "Considering your current surroundings, indicate to what extent do they hinder you or prevent you from performing daily routines?" Answers range from 0 to 10.
 3. "Are you currently with someone?" Answers are either 0 or 1 (0=No; 1=yes).

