Hypothesis 1: Lower levels of weekly and daily PA will be associated with a greater number of physical and social environmental barriers and less social participation.

Since PA is measured by Actiwatch objectively and self-reported by CHAMPS, we will first compare them with correlation analyses and identify the correlation coefficient. We will then use separate linear regression models to evaluate if environmental barriers (MQE) and social participation (PROMIS) predict PA, adjusting for baseline co-variates and potential confounders. Separate models will be used for the two different PA measurements - CHAMPS and Actiwatch.

Table 5.

Variables	Measures
PA(outcome)	Actiwatch – weekly and daily average counts
	CHAMPS – weekly energy expenditure (kcal/wk)
Environment	MQE – summary score of environment barriers/facilitators
	Momentary assessment – daily perception of environmental barrier (3 questions)
Social participation	PROMISE – summary score of participation ability and satisfaction
	Daily assessment – daily satisfaction with participation (3 questions)

We will then explore if the perception of environment barriers to PA and participation and satisfaction with participation fluctuate daily. Longitudinal analysis models will be built with time as covariate and each of these variables as the outcome. These variables are assessed daily during the home monitoring period by 6 separate questions adapted from validated questionnaires. We expect study participants' answers to some if not all of these questions to vary daily. We will

[figure not shown]
then build separate predictive models using hierarchical linear modeling (HLM) if change in the perception of the environment or satisfaction with participation is associated with PA (Actiwatch daily average counts). The HLMs will allow us to fully utilize the repeated measures of the environment, participation, and PA within each day.

Aim 2: To pilot a randomized-controlled trial to test the efficacy of an individually tailored lifestyle-based PA intervention. An intent-to-treat analysis will be applied to avoid various misleading artifacts that can arise in the trial; all subjects initially enrolled in the trial will be accounted for based on the group they were randomized into. Baseline comparison of the control and intervention groups will be done with ANOVA on PA, participation, and all the co-variates. We will consult our statistician for analysis guidance.

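### Aim 1 asks whether daily ratings fluctuate, but a time covariate only shows a pattern shared across participants; report within-person variation instead

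*Combined protocol and SAP*

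**What the plan says.** In the combined protocol and SAP, Statistical Analysis, Primary analyses, Aim 1, the question is: "We will then explore if the perception of environment barriers to PA and participation and satisfaction with participation fluctuate daily". The next sentence gives the method: "Longitudinal analysis models will be built with time as covariate and each of these variables as the outcome". The same paragraph adds an expectation: "We expect study participants' answers to some if not all of these questions to vary daily". The Measures section (Primary outcomes, b, item 1) asks the same thing of satisfaction, which "will be additionally investigated to see if it fluctuates daily and if it is associated with daily PA level".

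After the time models, the plan will "then build separate predictive models using hierarchical linear modeling (HLM) if change in the perception of the environment or satisfaction with participation is associated with" daily Actiwatch counts. That step concerns association with activity, not the amount of variation. The per-person plots under Univariate analyses are there to find outliers.

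Six items are involved. Three satisfaction items, scored 1 to 5, go into the logbook once a day. Three environment items are entered on the Actiwatch five times a day (Co-variates, predictors and confounders, 1b): two are scored 0 to 10, and the third, "Are you currently with someone", is scored 0 or 1. Table 5 counts all three environment items as perception of a barrier.

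The plan does not state how time is coded, which random effects are used, which parameter answers the question, or that a within-person variance or ICC will be reported.

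**The concern.** Fluctuation is variation within a person around that person's own level. A fixed effect of time describes how the average over participants moves across study days. One person may be up on day 2 and another on day 5, and the average can stay flat while every individual varies widely.

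If the time coefficient is taken as the answer, two errors are possible. Large person-specific variation can be reported as no fluctuation. A drift common to everyone, for example from getting used to being monitored, can be reported as fluctuation although it says nothing about how much individuals vary. The 0/1 company item adds a smaller problem: it is neither a barrier rating nor a continuous outcome.

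**Working it through.** The plan gives no figure for this step, so there is none to reproduce. The check is whether a time effect responds to the amount of day-to-day variation.

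**Inputs from the plan.** About 70 participants ("We will recruit approximately 70 veterans who have known diabetes and are aged ≥ 60 years"), both arms together at baseline, and 7 days of home monitoring.

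**Assumptions not in the plan.** Two-sided 5% level; one rating per day; between-person SD σ_b = 1, which sets the unit; within-person day-to-day SD σ_w from 0.5 to 3; 4,000 simulated data sets per setting.

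**Model.** Rating of person i on day j = μ + u_i + f(j) + e_ij, with SD(u) = σ_b and SD(e) = σ_w. The fluctuation question is about σ_w, or ICC = σ_b²/(σ_b² + σ_w²). The time effect tests only whether f is flat.

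**Step 1: no shared pattern.** With σ_b = 1 the ICC is 1/(1 + σ_w²). The last three columns give the share of runs with a significant time effect.

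| σ_w | ICC | Linear day | Categorical day | Mean of individual slopes |
|---|---|---|---|---|
| 0.5 | 0.80 | 5.1% | 5.2% | 5.3% |
| 1 | 0.50 | 5.1% | 4.8% | 4.9% |
| 2 | 0.20 | 5.3% | 4.5% | 5.1% |
| 3 | 0.10 | 5.1% | 4.9% | 5.5% |

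Simulation error is about ±1.96 × √(0.05 × 0.95/4000) = ±0.7 percentage points, so every entry is compatible with 5%. In the same data sets the within-person SD was recovered as 0.50, 1.00, 2.00 and 3.00.

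**Step 2: a shared linear drift of 0.1 per day.** With days centred at −3 to 3, the sum of squares is 9 + 4 + 1 + 0 + 1 + 4 + 9 = 28. So SE = σ_w/√(70 × 28) = σ_w/44.27, and power = Φ(0.1/SE − 1.96).

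| σ_w | 0.1/SE | Power by formula | Power by simulation |
|---|---|---|---|
| 0.5 | 8.85 | 100% | 100% |
| 1 | 4.43 | 99% | 99% |
| 2 | 2.21 | 60% | 60% |
| 3 | 1.48 | 31% | 31% |

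σ_w enters only through the standard error, so more fluctuation makes a significant time effect less likely.

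**Step 3: structured patterns, σ_w = 1.**

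| Pattern | Linear day | Categorical day | Mean of individual slopes |
|---|---|---|---|
| Weekend rise of 0.5, all start on the same weekday | 97% | 98% | 97% |
| Weekend rise of 1, start days staggered | 6.6% | 5.3% | 5.1% |
| Rise of 1 on study days 3 to 5, shared by all | 2.9% | 100% | 5.4% |
| Person-specific slopes, mean 0, SD 0.3 per day | 22.3% | 7.5% | 5.1% |

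The time effect picks up a pattern when it lines up with study day and the coding suits its shape. A weekend effect is missed once start days differ; the plan does not fix the start day. The 22.3% arises because a random-intercept model understates the standard error of the slope when slopes vary between people. With individual slopes allowed for, the rate returns to 5.1%.

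**Step 4: items entered five times a day.** Each person can give 5 × 7 = 35 readings. With a person intercept alone, the residual SD mixes swings within a day with changes between days. A daily mean of five readings varies around the person's level with variance σ_day² + σ_within-day²/5, so averaging reduces the mixing, and a day-within-person level removes it.

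**The case against.** The best defence is that the text is brief rather than wrong. It mentions neither a slope nor a rule that a non-significant slope means no fluctuation. Categorical day would find shared non-linear patterns, and the same longitudinal model yields a within-person residual variance if someone reports it. Step 1 is true by construction: data without a shared pattern will return about 5% under any valid test of one. The SDs are assumed. The step is described as exploratory, and the plan already expects answers to vary.

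Most of this stands and limits the point. What it does not remove is that the stated method targets a different quantity from the stated question, under either coding of time, and that no section plans the quantity that would answer it.

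Three stronger readings are tempting, and the documents do not support them:

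- A reader might infer that the plan is bound to answer no. Without a stated coding or decision rule, that does not follow.
- A reader might infer linear time from the single days term in the mixed model under Hypothesis 2a. That model is for activity counts at 6 months, and nothing carries it over to this step.
- A reader might infer that the hierarchical models or the tailoring depend on the result. The models are planned regardless; the conditional wording introduces the association to be tested. The tailoring uses each participant's own activity pattern, momentary entries and logbook.

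On the company item, the plan does not commit to a continuous model, and generalized mixed models are named under the additional analyses for Aim 2. Naming one for this item is a clarification. Table 5's listing of it among the barrier questions is an inconsistency in the text itself.

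**Conclusion.** The concern holds in a limited form. The time coefficient does not answer the fluctuation question. Used as the criterion, it would be non-significant in about 95% of studies without a shared pattern, whether the ICC were 0.80 or 0.10, and it could also present a shared drift as fluctuation. That insensitivity does not depend on the assumed SDs, because the test concerns the mean pattern only. The percentages in steps 2 and 3 do depend on the assumed SDs, effect sizes and start days.

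The consequence is confined to one exploratory Aim 1 question, raised in both the Measures and Statistical Analysis sections. The Aim 2 treatment comparison is untouched. The change is worth making because the same data can answer the question directly at almost no cost.

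**What to change.** Amend the Aim 1 analysis text as follows.

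- For each item, fit a mixed model with a random intercept for person. Report the between-person SD, the day-to-day within-person SD and the ICC, each with a 95% CI, and name these as the answer to the fluctuation question.
- For the environment items entered five times a day, add a day-within-person level, or analyse daily means, so that swings within a day are kept apart from changes between days.
- Include day of week (weekday or weekend) as a categorical term. Keep study day only as a check for drift over the monitoring week.
- Analyse the 0/1 company item with a logistic mixed model, and list it in Table 5 separately from the barrier ratings.

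The cost is SAP wording and slightly more analysis, with the same data and software. One limit remains: for the once-daily satisfaction items, day-to-day variation cannot be separated from measurement error. Their variance components will be less precise, and the report should say that the within-person SD contains both.

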2. The research assistant (RA) will guide the participants to complete a packet of survey questions. The questionnaires will ask about demographics, co-morbidities, physical activity (self-reported), *social participation*, their perception of the influence of contextual environment (physical and social environment) on daily lives, and potential barriers and facilitators of diabetes care.
3. The RA will direct the participants to complete a standardized education module, where they will learn to use the wrist-worn accelerometer to rate their response to pre-determined questions using a numerical

rating scale and entering responses, and to record addition information on activities and /or barriers or facilitators to PA in an accompanying logbook. [name] group has already refined this education module to teach older veterans with osteoarthritis and low back pain to use a similar accelerometer and logbook to obtain data on PA and symptoms. We will adapt [name] education module for this study. The accelerometers are designed for assessment of PA patterns over time and will be worn by each participant in their home environment for 7 continuous days (allowing capture of data on both weekdays and weekends). At five pre-determined times throughout the day, the accelerometers will prompt the participants to enter responses to 3 pre-determined questions to assess their perception of the contextual environment on their ability to participate in PA and social activities (i.e., momentary assessment of the environment). Based on experience by [name] group, we will set the accelerometer alarm at wake up time, 11am, 3pm, 7pm, and before bedtime. Time for waking up and going to bed will be individualized for each participant. Each participant will know when their accelerometer alarm will go off. This will help the participant to pay attention to the alarm.

- Participants will become familiar with an accompanying logbook, in which participants will record the exact environment and activities they were involved in at two-hour intervals (See Appendix for the mock Activity Log). The logbook provides supplementary data that are important for the tailoring intervention, and also serves to cross-validate the items entered in the accelerometer. The logbook will be used as a back-up if there are missing data from the accelerometer.

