An occupational therapist (OT) will deliver the intervention; this OT will have undergone training by [name] group to deliver standardized lifestyle-based PA intervention using accelerometer –measured PA patterns. [name] group has already established standardized training protocol for OT to deliver this type of tailoring intervention. Additionally, as discussed in the Background, OT's approaches to lifestyle intervention are most befitting for this population (older, high risk for disability, sedentary, restricted by their environment, etc.). In the future, we will test the intervention delivery through other trained providers such as a nurse educator. For the study, the participant will meet with an OT for a one-hour session for the following activities:

1. Brief presentation on the benefits of PA and how to safely perform PA at an older age and with diabetes. Each participant will leave the session with a National Institute of Aging exercise workbook⁶⁷ and tips to exercise safely with diabetes.⁶⁸
2. The OT will review the baseline PA pattern report determined from the home monitoring period. This report is prepared before the counseling session. It also summarizes the participant's self-reported perception of the environment, his/her daily activities and the associated context. The OT will help the participant to correlate the level of PA with potential barriers associated with PA at that moment. For example, being alone may be associated with few activities, but attending church is associated with more activities. The OT will focus on periods where the relationship between PA and an identifiable and modifiable barrier is most salient. (See Appendix for a mock Baseline Physical Activity Report)

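### The Aim 1 hierarchical model does not define change in the daily ratings or say how ratings enter, so its slope may mix between-person and day-to-day associations

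*Combined protocol and SAP*

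**What the plan says.** Under Statistical Analysis, Primary analyses, Aim 1, the plan first runs person-level linear regressions of physical activity (PA) on the environment questionnaire (MQE) and the participation questionnaire (PROMIS). It then explores whether the daily ratings fluctuate: "Longitudinal analysis models will be built with time as covariate and each of these variables as the outcome". Finally it builds hierarchical linear models to see "if change in the perception of the environment or satisfaction with participation is associated with PA (Actiwatch daily average counts". The only further description of these models is "The HLMs will allow us to fully utilize the repeated measures of the environment, participation, and PA within each day".

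The Measures section gives daily satisfaction with participation the same day-level purpose: it "will be additionally investigated to see if it fluctuates daily and if it is associated with daily PA level". Hypothesis 1 covers both levels at once: "Lower levels of weekly and daily PA will be associated with a greater number of physical and social environmental barriers and less social participation".

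The text contains no model equation, no definition of change, no person-mean term or centring, no person fixed effects and no random-effects structure for these models.

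**The concern.** The question put to the hierarchical model is about days within a person. The between-person question already has its own regressions on MQE and PROMIS, so what the hierarchical model adds is the day-level link.

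A random intercept does not isolate that link. If a daily rating is entered as recorded, one coefficient has to represent two different comparisons. Suppose people in poorer health rate their surroundings worse and are also less active. The coefficient can then be negative and significant although nobody moves less on their own worse days. Hypothesis 1 itself predicts a person-level association of this kind, so it is not a remote case.

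The preceding step does not help. Modelling each rating as an outcome with time as covariate looks for a trend over the week; it does not split the rating when the rating later becomes a predictor.

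At stake is what Aim 1 may conclude about day-to-day links between surroundings, satisfaction and activity, and what is carried forward from it when a larger trial is designed.

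**Working it through.** The plan states no power, effect size, alpha, ICC or variance for these models, so it has no figure to reproduce.

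**Inputs from the documents**
- Days per person: T = 7. The accelerometers "will be worn by each participant in their home environment for 7 continuous days" (Research Procedures, step 3).
- Environment ratings: "the study participants will enter their perception of the physical and social environment, into the accelerometer 5 times a day" (Co-variates, item 1b). Satisfaction ratings are recorded once a day (Measures).
- People: about 70 (Sample). 56 was also tried, as 2 × 28, from the 28–35 per group given under Hypothesis 2a.

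**Assumed, because the documents are silent:** rating ICC (ρx), activity ICC (ρy), the strength of the person-level link, two-sided 5% tests, and no covariates.

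**Step 1: weight of the between-person slope.** In a random-intercept model with the uncentred rating as sole predictor, the coefficient is w × (between slope) + (1 − w) × (within slope), where

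- Iw = (T − 1)(1 − ρx)/(1 − ρy)
- Ib = [ρx + (1 − ρx)/T] / [ρy + (1 − ρy)/T]
- w = Ib/(Ib + Iw)

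ρx = ρy = 0.5: Ib = 1, Iw = 6, so w = 1/(1 + 6) = 0.14.
ρx = 0.7, ρy = 0.5: Ib = 0.743/0.571 = 1.3, Iw = 6 × 0.3/0.5 = 3.6, so w = 1.3/4.9 = 0.27.

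| w at T = 7 | ρy 0.3 | ρy 0.5 | ρy 0.7 |
|---|---|---|---|
| ρx 0.3 | 0.14 | 0.08 | 0.04 |
| ρx 0.5 | 0.25 | 0.14 | 0.07 |
| ρx 0.7 | 0.42 | 0.27 | 0.14 |

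**Step 2: false-positive rate when the true day-level slope is zero** (uncentred rating, 70 people × 7 days, 1000 runs per setting, random-intercept REML).

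Varying the person-level slope, residual activity ICC 0.5:

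| Person-level slope | ρx 0.3 | ρx 0.5 | ρx 0.7 |
|---|---|---|---|
| 0 | about 5% | about 5% | about 5% |
| −0.2 | 7% | 9% | 14% |
| −0.4 | 9% | 18% | 38% |

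Varying instead the person-level correlation r between stable rating and stable activity:
- ρx = ρy = 0.5: 4.9% (r = 0), 13% (r = −0.3), 30% (r = −0.5), 57% (r = −0.7).
- ρx = 0.7, ρy = 0.5: 24% (r = −0.3), 59% (r = −0.5).
- ρx = 0.7, ρy = 0.3: 69% (r = −0.5).
- With 56 people and r not zero: 14% to 59%.

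Cross-check of step 1 against step 2 at ρx = ρy = 0.5, r = −0.5: the slope on the person mean is −0.25/0.571 = −0.44, and 0.143 × −0.44 = −0.063. The simulated mean slope was −0.063.

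**Step 3: other ways of entering the rating.** With a person mean plus a daily deviation, the deviation test rejected in 4.1% to 6.2% of runs over all correlation settings, with a mean estimate within 0.004 of zero. With day-to-day differences as the predictor, rejection was 3.6% to 6.3%.

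**Step 4: prompt-level records.** Five prompts on 7 days give T = 35. The weight falls to 1/(1 + 34) = 0.03 at ICCs 0.5/0.5, and to 1.378/(1.378 + 20.4) = 0.06 at 0.7/0.5. With a person-level slope of −0.4, false-positive rates were 7% and 14%, against 18% and 38% on daily records. This applies only to the environment ratings, and only if activity is also summarised around each prompt; the outcome the plan names is the daily average.

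**The case against.** The strongest reply is that the plan never says ratings will be entered as recorded. It names the predictor as change, and a reader may fairly take that to mean a difference or deviation score. On that reading the error rate is close to nominal (step 3) and most of the problem goes. This stands: the fault is an unspecified model. A reader might infer that the plan has committed to the wrong one, and the documents do not support that.

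A second tempting inference is that the tailoring is compromised, since the therapist session under Intervention, item 2, works with momentary links: "The OT will help the participant to correlate the level of PA with potential barriers associated with PA at that moment". That step uses one participant's own report, prepared before the session from that person's monitoring week, so between-person mixing cannot arise in it. Nothing in the documents feeds a pooled coefficient into any report, strategy or goal. Nor does the model enter the Aim 2 comparison.

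Third, the analysis is exploratory. It sits under the Primary analyses heading, but its own text introduces it as exploration, the momentary data are described as exploratory, and no decision rule attaches to it. This limits the severity and leaves the ambiguity in place.

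Fourth, global health, co-morbidities and depression are measured, and adjusting for them would shrink the person-level contamination. Adjustment is stated for the preceding linear regressions and not explicitly for the hierarchical models, and it would remove only the measured part.

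Finally, any single false-positive figure depends on assumptions. That is also correct, and only a range can be given.

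**Conclusion.** The concern holds in a limited form. The plan asks a day-level question of a model whose key predictor it does not define. If ratings enter uncentred, the between-person slope takes roughly 4% to 42% of the weight at 7 days per person, for ICCs between 0.3 and 0.7. With no true day-level link, false-positive rates are about 5% when there is no person-level link, roughly 10–40% under moderate assumptions, and up to 69% in the strongest setting tried. They would be lower for environment ratings analysed by prompt. The ICCs and the person-level link are assumptions, so the actual rate for this study is undetermined.

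The consequence is confined to how the exploratory Aim 1 day-level association is read. It is worth correcting because the remedy is nearly free.

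**What to change.** In the Aim 1 section, define change and write out the model. Enter each rating as two terms: the person's 7-day mean, and the daily deviation from that mean (prompt-level deviation if activity is analysed by prompt). State which time unit applies to each rating, since satisfaction is daily and the environment items are recorded five times a day. Use only the deviation coefficient to answer the change question, and report the person-mean coefficient separately as the between-person association. State the random-effects structure and whether the listed confounders are included.

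Cost: one extra term per model and a few sentences of text. No new data, visits or participants.
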